5.3.1.1. Date of Last Dose of Study Treatment

No imputation will be done for first dose date. Date of last dose of study treatment, if unknown or partially unknown, will be imputed as follows:

• If the last date of study treatment is completely missing and there is no End of Treatment (EOT) CRF page and no death date, the patient should be considered to be ongoing and use the data cutoff date for the analysis as the last dosing date; or

• If the last date of study treatment is completely or partially missing and there is either an EOT CRF page or a death date available (on or prior to the data cutoff date), then impute this date as the last dose date:

= 31DECYYYY, if only Year is available and Year < Year of min (EOT date, death date),

= Last day of the month, if both Year and Month are available and Year = Year of min (EOT date, death date) and Month < the month of min (EOT date, death date), or

= min (EOT date, death date), for all other cases.

5.3.1.2. Missing or Partial Death Dates

Missing or partial death dates will be imputed based on the last contact date:

- If the entire date is missing it will be imputed as the day after the date of last contact; or
- If the day or month is missing, death will be imputed to the maximum of the full (nonimputed) day after the date of last contact and the following:
 - Missing day: First day of the month and year of death, or
 - Missing day and month: January first of the year of death.

5.3.1.3. Date of Start of New Antineoplastic Therapy

Incomplete dates for new antineoplastic therapy will be imputed as follows and will be used to determine censoring dates for efficacy analyses:

- The end date of new antineoplastic therapy will be included in the imputations for start date of new antineoplastic therapy. If the end date of new antineoplastic therapy is
 - completely missing then it will be ignored in the imputations below
 - partially missing with only year (YYYY) available then the imputations below will consider 31DECYYYY as the end date of the new antineoplastic therapy
 - partially missing with only month and year available then the imputations below will consider the last day of the month for MMMYYYY as the end date of the new antineoplastic therapy

For patients who have not discontinued study treatment at the analysis cut-off date, last dose of study treatment is set to the analysis cut-off date in the imputations below.

If the start date of new antineoplastic therapy is completely or partially missing then the imputed start date of new antineoplastic therapy is derived as follows:

• Start date of new antineoplastic therapy is completely missing

- Imputed start date = min [max(PD date + 1, last dose of study treatment + 1), end date of new antineoplastic therapy]
- Only year (YYYY) for start of antineoplastic therapy is available

IF YYYY < Year of min [max(PD date + 1, last dose of study treatment + 1), end date of new antineoplastic therapy] THEN imputed start date = 31DECYYYY;

ELSE IF YYYY = Year of min [max(PD date + 1, last dose of study treatment + 1), end date of new antineoplastic therapy]

THEN imputed start date = min [max(PD date + 1, last dose of study treatment + 1), end date of new antineoplastic therapy]

ELSE IF YYYY > Year of min [max(PD date + 1, last dose of study treatment + 1), end date of new antineoplastic therapy]

THEN imputed start date = 01JANYYYY

• Both Year (YYYY) and Month (MMM) for start of antineoplastic therapy are available

IF

YYYY = Year of min [max(PD date + 1, last dose of study treatment + 1), end date of new antineoplastic therapy], AND

MMM < Month of min [max(PD date + 1 day, last dose of study treatment + 1 day), end date of new antineoplastic therapy]

THEN

imputed start date = DAY (Last day of MMM) MMM YYYY;

ELSE IF

YYYY = Year of min [max(PD date + 1, last dose of study treatment + 1), end date of new antineoplastic therapy], AND

MMM = Month of min [max(PD date + 1 day, last dose of study treatment + 1 day), end date of new antineoplastic therapy]

THEN

imputed start date = min [max(PD date + 1 day, last dose of study treatment + 1 day), end date of new antineoplastic therapy]);

ELSE IF

YYYY = Year of min [max(PD date + 1, last dose of study treatment + 1), end date of new antineoplastic therapy], AND

MMM > Month of min [max(PD date + 1 day, last dose of study treatment + 1 day), end date of new antineoplastic therapy]

THEN

imputed start date = 01 MMM YYYY;

ELSE IF

YYYY < Year of min [max(PD date + 1, last dose of study treatment + 1), end date of new antineoplastic therapy]

THEN

imputed start date = DAY (Last day of MMM) MMM YYYY;

ELSE IF

YYYY > Year of min [max(PD date + 1, last dose of study treatment + 1), end date of new antineoplastic therapy]

THEN

imputed start date = 01 MMM YYYY.

5.3.1.4. AE Stop Date:

Ongoing events will have the AE Stop Date set to one of the following values:

- If the day or month is missing, AE Stop Date will be imputed the same way as that in Section 5.3.1.5.
- Date of Death, if imputed date is after date of death.
- If the date is completely missing, no imputation will be performed.

Adverse Events are deemed similar if they have the same verbatim term.

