5.4. Safety Follow-Up

All patients will have safety follow-up after permanent discontinuation of randomized study drug treatment (enzalutamide plus leuprolide, enzalutamide monotherapy, or placebo plus leuprolide). Safety follow-up should occur approximately 30 days after the last dose of randomized study drug treatment.

In the event that antineoplastic treatment is initiated before safety follow-up occurs (eg, a physician not associated with protocol MDV3100-13(C3431004) initiates the treatment, and study site personnel are not aware of the treatment until afterward), safety follow-up should be scheduled as soon as possible.

If treatment is discontinued due to an adverse event or serious adverse event, the event(s) must be followed up as described in [Section 8.5.6](#). Patients who discontinue study drugs due to adverse events are encouraged to continue long-term follow-up in the clinic ([Section 5.5](#)).

For patients who refuse further clinic study visits, telephone contact should be attempted and documented to review for adverse events through approximately 30 days after the last dose of randomized study drug treatment. If the patient does not respond to or refuses telephone contact, the patient's medical records from the treating physician may be reviewed. If all methods fail, the procedures for loss to follow-up in [Section 5.6](#) should be followed.

Safety follow-up procedures are listed in [Table 8](#). The visit window is -3 to +10 days from the last dose of randomized study drug treatment. For patients who permanently discontinue study treatment during the suspension period, the safety follow-up visit may be scheduled any time after 28 days post the last dose of randomized study drug treatment.

Table 8. Safety Follow-Up Procedures

Activity/Assessment	Comment
General Activities	
Vital signs and complete physical examination	Measure blood pressure, heart rate, temperature, and weight. Assess systems per standard of care at the study site and as clinically indicated by symptoms.
ECOG performance status	Refer to Table 13 .
BPI-SF, FACT-P, EQ-5D-5L, and QLQ-PR25 questionnaires	Refer to Appendix 117 , Appendix 2 , Appendix 3 , and Appendix 4 .

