3.4. Baseline Variables

3.4.1. Study Drug, Study Treatment, and Baseline Definitions

The date of first dose (start date) of study treatment in the combination arms is the earliest date of non-zero dosing for each of the study drugs (enzalutamide/placebo or leuprolide).

The date of first dose (start date) of study treatment in the enzalutamide monotherapy arm is the earliest date of non-zero dosing of enzalutamide.

The date of last dose of study treatment in the combination arms is the latest date of non-zero dosing for each of the study drugs.

The date of last dose of study treatment in the enzalutamide monotherapy arm is the latest date of non-zero dosing of enzalutamide.

Definition of Baseline:

No windowing will be applied when defining baseline. For example, the protocol requires safety assessments to be performed within 28 days prior to randomization; however, values outside this window will not be excluded when determining baseline assessments. Any deviations from the protocol specified window will be documented as protocol deviations.

Definition of baseline for efficacy and baseline analyses

The last measurement prior to randomization will serve as the baseline measurement for efficacy and baseline analyses.

Definition of baseline for PRO

Per protocol, the first PRO assessment is planned to occur prior to dosing on Day 1; therefore, the last measurement on or prior to the day of first dose of study treatment (on or prior to randomization for patients randomized but not dosed) will be used as the baseline measurement.

Definition of baseline for safety analyses

The last available assessment on or prior to the date of first dose of study treatment (or prior to randomization for patients randomized but not dosed) is defined as the 'baseline' value or 'baseline' assessment for safety analyses. If an assessment is planned to be performed prior to the first dose of study treatment in the protocol and the assessment is performed on the same day as the first dose of study treatment, it will be assumed that it was performed prior to study treatment administration, if assessment time is not collected or is missing. If assessment times are collected, the observed time point will be used to determine pre-dose on study Day 1 for baseline calculation (this only applies for safety). Unscheduled assessments will be used in the determination of baseline.

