without evidence of metastasis will be censored at the last adequate assessment prior to initiation of such therapy. (Note: if progression occurs on the same date as the start of such therapy the progression will count as an event.) Additionally patients with documented progression or death after 2 or more missing tumor assessment will be censored at the last adequate assessment prior to the missing assessments. In this study, tumor assessments are assessed every 24 weeks. Therefore, time without adequate assessment is defined as 49 weeks (allowing for a +/-1 week window for assessments). The censoring rules for the primary and sensitivity analyses of MFS are summarized in Table 7.

Analysis	Censoring Rules	Date of Censoring
Primary analysis of MFS	Patients with no baseline or no post baseline assessments who have not died within 49 weeks after randomization	Date of randomization
	Patients who were randomized but confirmed metastatic at baseline	Date of randomization
	Patients who had no confirmed metastasis and did not die prior to data cutoff date	Date of the last adequate radiographic tumor assessment prior to data cutoff date
	Patients who initiate antineoplastic therapy such as cytotoxic chemotherapy, abiraterone acetate, hormonal agents, prostate cancer vaccines, nonradioactive bone-targeting agents and systemic radiopharmaceuticals for prostate cancer, or any antineoplastic therapy without evidence of metastasis	Date of the last adequate radiographic tumor assessment prior to first use of any such therapy
	Patients with radiation therapy performed for prostate cancer-related lesions without evidence of metastasis	Date of the last adequate radiographic tumor assessment prior to the earliest use of radiation therapy
	Patients with evidence of metastasis or death after 2 or more consecutive missed tumor assessment visits	Date of the last adequate radiographic tumor assessment prior to the first missed visit date

Table 7. The Censoring Rules for the Primary and Sensitivity Analyses of MFS

MFS = Metastatic Free Survival; of note, the censoring rules are applied to MFS events by either radiographic progression, or death due to any cause without evidence of radiographic progression; of note, antineoplastic therapies according to the above search criteria undergo medical review to confirm.

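### When a new-therapy start date is completely missing, SAP 5.3.1.3 dates therapy at about week 37 for a man without PD who discontinued during suspension, whenever it truly began

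*SAP*

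**What the plan says.** SAP 5.3.1.3 gives the rule for a completely missing start date: "Imputed start date = min [max(PD date + 1, last dose of study treatment + 1), end date of new antineoplastic therapy". An end date that is itself "completely missing then it will be ignored in the imputations below", so it then sets no upper limit. The section says that the resulting dates "will be used to determine censoring dates for efficacy analyses".

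Last dose means the last capsule or injection actually taken. SAP 3.4.1 states, for one arm, "The date of last dose of study treatment in the enzalutamide monotherapy arm is the latest date of non-zero dosing of enzalutamide", and the combination arms are defined in the same way. There is no adjustment for suspension. The only special case in 5.3.1.3 is for men who have not discontinued at the cut-off, for whom "last dose of study treatment is set to the analysis cut-off date".

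Under SAP 2.2, men with undetectable PSA at week 36 stop study drug at week 37. Protocol 5.4 foresees that some will never restart: "For patients who permanently discontinue study treatment during the suspension period, the safety follow-up visit may be scheduled any time".

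For primary MFS, Table 7 in SAP 6.1.1.1 censors a man who starts new therapy without metastasis at the "Date of the last adequate radiographic tumor assessment prior to first use of any such therapy".

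**The concern.** For a man treated continuously, the day after the last dose is a fair stand-in for the earliest date at which new therapy could have begun. For a man who suspended, it is not. He may be off drug, under observation and metastasis-free for years before he discontinues for good and starts something else. The rule still anchors on the last dose before suspension.

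Three analyses use the date. In time to first use of new antineoplastic therapy, which was alpha-controlled at the primary analysis (SAP 5.1.3), the imputed date is the event time itself. In primary MFS it fixes the censoring scan. In PFS2, the notes to Table 9 (SAP 6.5.1) limit the censoring scan for a man without PD to scans on or before the therapy start. The SAP adjusts for suspension when it defines treatment periods (3.5) and durations (5.2.5), and it anchors missing death dates to last contact (5.3.1.2). It does neither here.

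**Working it through.** **The plan's own figure.** With 142 events, hazard ratio 0.58 and two-sided alpha 0.05, power = Φ(|ln 0.58| × √(142/4) − 1.96) = Φ(0.5447 × 5.958 − 1.96) = Φ(1.286) = 0.90. This agrees with SAP 5.1.1, and the date rule does not change it.

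**Inputs.** Study day = (week − 1) × 7 + 1 (SAP 5.2.7), so week 25 is day 169, week 37 is day 253 and week 49 is day 337. Scans fall at week 25, week 49 and every 24 weeks after that (Protocol Appendix 5). One month is 30.4375 days (SAP 5.2.6).

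**The affected case.** The start date is completely missing, there is no PD date, the man discontinued during suspension, and the therapy end date is missing or late. Take the last dose as day 252.
- Imputed start = 252 + 1 = day 253; 253/30.4375 = 8.3 months.
- The last scheduled scan before it is day 169; 169/30.4375 = 5.6 months. Any last dose from day 246 to day 258 gives the same scan.

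**A true start at month 40.** 40 × 30.4375 = day 1217. The last scan before it is 169 + 6 × 168 = day 1177, or 38.7 months. Therapy is dated (1217 − 253)/30.4375 = 31.7 months too early, and (1177 − 169)/30.4375 = 33.1 months of MFS follow-up are lost.

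| True start (month) | Start dated too early by (months) | MFS censored under true date (month) | MFS time lost (months) |
|---|---|---|---|
| 12 | 3.7 | 11.1 | 5.5 |
| 24 | 15.7 | 22.1 | 16.6 |
| 36 | 27.7 | 33.1 | 27.6 |
| 48 | 39.7 | 44.2 | 38.6 |
| 60 | 51.7 | 55.2 | 49.7 |

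**Where the rule does not do this.**
- *PD recorded.* The PD term takes over: PD at month 48 puts therapy one day later, and the PD counts as an event.
- *Year only, later than the last-dose year.* The date becomes 1 January of the recorded year, at most 364/30.4375 = 12.0 months early. In the last-dose year itself the true start lies in that same year, so the error is under 12 months.
- *Month and year known.* The date stays within the recorded month, so the error is at most about 1 month.
- *Not discontinued at cut-off.* Therapy is dated at cut-off + 1, about month 90 on the planned study length. This should be rare: new therapy is recorded after discontinuation (Protocol 9.1.3.2), and chemotherapy or an antiandrogen forces discontinuation (Protocol 7.2).

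**Overall size (assumed inputs).** The documents do not give the number of such men. Assume 350 men in an arm with 50 months' mean follow-up, which is 17,500 person-months.
- One man losing 20 months is 20/17,500 = 0.1% of the arm's time. Ten men losing 60 months each is 600/17,500 = 3.4%.
- A narrower scenario assumes that 80% and 60% of men suspend, that half of therapy starts in suspended men come without a restart, and that 2–10% of start dates are missing. It gives about 0.6–3.4 men per arm, dated about 24 months early on average. At the top of that range, 3.4 × 24 = 82 person-months, or 0.5%.
- Under constant hazards, with that loss in the enzalutamide arm only, 0.58 becomes 0.58/(1 − 0.0047) = 0.583. If both arms are affected, the shifts partly cancel. A Cox simulation of the scenario (control hazard 0.008 per month, hazard ratio 0.6) moves the hazard ratio by about 0.001 or less on average.
- The extreme of ten men losing 60 months each, all in that one arm, would give 0.58/(1 − 0.034) = 0.60.

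**The case against.** The strongest reply is that this is an edge case with no demonstrated consequence. Four conditions must hold together, and nothing in the documents shows that any man meets them. Sensitivity 1 (SAP 6.1.1.3) already keeps events after new therapy. The primary analysis is complete (Protocol 3.1), and at the final OS analysis only OS is formally tested (SAP 5.1.2). OS is censored at last contact, not at therapy start. All of this stands, and it limits the point to a small correction.

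Three stronger readings are tempting, and the documents do not support them.
- *Any missing start date is wrong by years.* The PD term and the partial-date branches prevent that.
- *MFS events are lost.* A man who starts therapy without metastasis is censored under his true date too, and Table 7 drops his later metastasis or death either way. What is lost is time at risk. If PD follows the true start, the error runs the other way: therapy is dated after PD, and an event is counted that the true date would have censored.
- *Only suspended men are affected, so the comparison is biased.* A man who stopped early for an adverse event and began new therapy much later meets the same anchor. Imbalance between arms is possible, because suspension depends on PSA response, but the documents do not show it.

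The reply also notes that a discontinuation-date anchor is not perfect. Protocol 5.4 mentions therapy begun by an outside physician and learned of afterwards, so that date can fall after the true start. This is a fair limitation. The error should usually be much smaller than one measured from week 37.

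**Conclusion.** The point holds in the narrow case. The stated rule gives a wrong date, and the direction is known: with no PD, the last dose before suspension as anchor and no early end date, therapy is always placed at about month 8.3. The clearest effect is on time to new antineoplastic therapy, where a month-40 event is scored at month 8.3. For MFS, and for PFS2 in a man still alive, the cost is follow-up cut back to month 5.6.

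The size per man rests only on the visit schedule and the true start date. The overall size rests on assumptions, because the number of completely missing start dates is not given. On plausible counts the change in the hazard ratio is probably negligible, and no conclusion of the trial is shown to change.

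There is one loose end. Section 5.3.1.3 does not say whether its PD date is by BICR or by the investigator. The conclusion that no MFS event is lost assumes BICR. If it is the investigator's, a man with progression on central reading only, between week 25 and his true therapy start, could have that event censored.

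**What to change.** In SAP 5.3.1.3:
- Replace the last-dose + 1 term, for any man who discontinued, with the latest of last dose + 1, the permanent-discontinuation (EOT) date and, where a dated contact recording no new therapy exists, the day after that contact. Applying this to every man who discontinued also covers early stops for adverse events.
- Cap the imputed start at the earlier of the therapy end date and the analysis cut-off, so that a therapy known to have started cannot be dated after the cut-off.
- State whether the PD date is by BICR or investigator for each endpoint that uses it.
- List the men whose start date was completely missing, with both the old and the new imputed date.

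Apply the change to the time-to-new-therapy and PFS2 updates at the final OS analysis. Because the primary analysis is complete, rerun MFS only as a supportive check.

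The cost is SAP wording and a small programming change. SAP 5.3.1.1 already uses an EOT date, but the team should confirm that, for a man who discontinued in suspension, it records the decision to stop and not the last dose. The documents do not show that a dated statement of no new therapy is collected, so that term applies only where the data exist. The remaining downside is that the EOT date can fall slightly after the true start when therapy was begun elsewhere.

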5.3.1.5. Other Missing or Partial Dates

Imputation methods for other partial dates as follows:

• If the day of the month is missing for a start date used in a calculation, the first day of the month will be used to replace the missing date.

- If both the day and month are missing, the first day of the year is used.
- For stop dates, the last day of the month, or last day of the year is used if the day or day and month are missing, respectively.
- If the date is completely missing, no imputation will be performed.

6. ANALYSES AND SUMMARIES

6.1. Primary Endpoint(s)

6.1.1. Metastasis-Free Survival (MFS) Between enzalutamide in combination with leuprolide versus placebo in combination with leuprolide

6.1.1.1. Primary Analysis

The primary efficacy analysis will compare MFS based on BICR assessment between enzalutamide in combination with leuprolide versus placebo in combination with leuprolide using a 2-sided stratified log-rank test as described in Section 5.1. The primary population for analysis will be the ITT population. Strata will be based on those specified in the randomization system.

MFS is defined as the time in months between randomization and the earliest objective evidence of radiographic progression as determined by BICR, or death due to any cause without evidence of radiographic progression, whichever occurs first. Radiographic assessment of soft tissue disease will be according to RECIST v1.1 on CT scan or on MRI. Additional bone lesions will be assessed separately using radionuclide bone scans.

Table 6 summarizes the protocol-specified rules for the radiographic evidence of progression.

Tissue Type	Method of Assessment	Schedule	Comment
Bone	A whole-body radionuclide bone scan will consist of 5 regions including skull, thorax, spine, pelvis, and extremities. Radiographic progression for bone disease is defined as the appearance of 1 or more metastatic lesion on bone scan. When bone lesions are found in a single region, confirmation with a second imaging modality (plain film, CT, or MRI) will be required. Appearance of metastatic lesions in 2 or more of the	Screening and every 24 weeks thereafter (earlier if progression is clinically suspected) until radiographic progression is confirmed by independent central radiology review	All study films should be read locally at the study site and submitted to the central imaging unit for independent central radiology review

Table 6.	Protocol-Specified Ru	ules for the Radiogran	hic Evidence of Progression
	riotocor specifica in	and for the reading rup	

Tissue Type	Method of Assessment	Schedule	Comment
	5 regions on a bone scan will not require confirmation with a second imaging modality.		
Soft Tissue	Assessment of soft tissue disease will be done by CT or MRI. Radiographic progression for soft tissue disease is defined by RECIST 1.1.		

 Table 6.
 Protocol-Specified Rules for the Radiographic Evidence of Progression

CT = computed tomography; MRI = magnetic resonance imaging; RECIST 1.1 = Response Evaluation Criteria in Solid Tumors version 1.1.

The treatment effect will be estimated using a Cox's Proportional Hazard model stratified by the randomization strata to calculate the hazard ratio. Each stratum will define a separate baseline hazard function, ie, for the i-th stratum the hazard function is expressed as: $h(i;t) = h(i,0;t) \exp(x\beta)$, where h(i,0;t) defines the baseline hazard function for the i-th stratum and x defines the treatment arm (0 = control arm, 1 = experimental arm) and β is the unknown regression parameter.

Ties will be handled by using the Exact option in SAS.

In addition, the 95% CIs for the hazard ratio will be reported at the final analyses for MFS.

Kaplan-Meier estimates (product-limit estimates) will be presented by treatment arm together with a summary of associated statistics including the median MFS time with 2-sided 95% CIs. The CIs for the median will be calculated according to Brookmeyer and Crowley (1982) and the CIs for the survival function estimates at the time points defined above will be derived using the log-log transformation according to Kalbfleisch and Prentice (2011) with back transformation to a CI on the untransformed scale. The estimate of the standard error will be computed using Greenwood's formula.

Frequency (number and percentage) of patients with each event type (PD or death) and censoring reasons will be presented by treatment arm.

For patients not known to have had radiographic progression and who have not died at the time of the analysis data cutoff, MFS time will be censored at the date of the last adequate assessment (see Section 5.2.4) on or before the analysis data cutoff date. For patients who were randomized but later confirmed to have metastatic disease at enrollment or who had no adequate postbaseline tumor assessment, information will be censored on the date of randomization. Patients who initiate antineoplastic therapy such as cytotoxic chemotherapy, abiraterone acetate, hormonal agents, prostate cancer vaccines, nonradioactive bone-targeting agents and systemic radiopharmaceuticals for prostate cancer, or any antineoplastic therapy

without evidence of metastasis will be censored at the last adequate assessment prior to initiation of such therapy. (Note: if progression occurs on the same date as the start of such therapy the progression will count as an event.) Additionally patients with documented progression or death after 2 or more missing tumor assessment will be censored at the last adequate assessment prior to the missing assessments. In this study, tumor assessments are assessed every 24 weeks. Therefore, time without adequate assessment is defined as 49 weeks (allowing for a +/-1 week window for assessments). The censoring rules for the primary and sensitivity analyses of MFS are summarized in Table 7.

Analysis	Censoring Rules	Date of Censoring
Primary analysis of MFS	Patients with no baseline or no post baseline assessments who have not died within 49 weeks after randomization	Date of randomization
	Patients who were randomized but confirmed metastatic at baseline	Date of randomization
	Patients who had no confirmed metastasis and did not die prior to data cutoff date	Date of the last adequate radiographic tumor assessment prior to data cutoff date
	Patients who initiate antineoplastic therapy such as cytotoxic chemotherapy, abiraterone acetate, hormonal agents, prostate cancer vaccines, nonradioactive bone-targeting agents and systemic radiopharmaceuticals for prostate cancer, or any antineoplastic therapy without evidence of metastasis	Date of the last adequate radiographic tumor assessment prior to first use of any such therapy
	Patients with radiation therapy performed for prostate cancer-related lesions without evidence of metastasis	Date of the last adequate radiographic tumor assessment prior to the earliest use of radiation therapy
	Patients with evidence of metastasis or death after 2 or more consecutive missed tumor assessment visits	Date of the last adequate radiographic tumor assessment prior to the first missed visit date

Table 7. The Censoring Rules for the Primary and Sensitivity Analyses of MFS

MFS = Metastatic Free Survival; of note, the censoring rules are applied to MFS events by either radiographic progression, or death due to any cause without evidence of radiographic progression; of note, antineoplastic therapies according to the above search criteria undergo medical review to confirm.

